7.3 Lost to Follow-Up

Participants classified as lost to follow-up (LTFU) need to meet both of the following criteria:

- Failure to respond or reply to 3 documented phone contact attempts, followed by
- Failure to respond to a certified letter sent to the address provided by the participant.

Only after documentation of these failed attempts to connect with the participant, will they be determined as LTFU. In scenarios in which a participant is relocated after 3 failed attempts, the study PI will address continued participation on a case-by-case basis.

8 STUDY ASSESSMENTS AND PROCEDURES

8.1 Efficacy Assessments

Remote Data Collection

Study visits may be conducted remotely (e.g., telephone, facetime) in the following situations:

- a participant is unable to attend a visit because of a debilitating illness; the site must inform the protocol team in advance
- the site is temporarily unable to conduct non-essential visits in the clinic per University policies at the time of the visit; the site must inform the protocol team in advance
- at the discretion of the protocol team if the risk of an on-site visit is felt to pose more risk than potential benefit to the participant; a message from the team will be sent to the study team

Regardless of the situation, the study team should designate which visits were conducted remotely and attempt to obtain as much of the visit-specific required information, based on the Schedule of Events, and record it on the relevant study specific checklist. The reason for conducting the visit remotely must also be recorded and documented in the participant's study file.

Visit Windows:

- Perform visits scheduled \leq 7 days apart per window listed in SOE. There is no window around Day 7 visit. There is a \pm 2 days window around the Day 14 Visit.
- All windows after Day 14 visit are $+$ / $-$ 7 days (6 in the case of overlapping visits). Please reference SOE. The protocol allows scheduling the Day 28 Leukapheresis outside the parameters of the visit window. Please reference SOE and sections 4.1 and 8.2.3.

Medical History:

The medical history must include all signs and symptoms and all diagnoses regardless of grade within the past 30 days prior to entry. Assessment and documentation of the medical history evaluation occurs at the screening visit. Update to medical history will occur at all clinical visits.

Document:

- All allergies to any medications and their formulations
- Date of birth, gender, race and ethnicity of participant
- Nadir CD4 and pre-ART HIV-1 RNA level, if available (if nadir documentation is not available, collect and record participant recall)
- Targeted Reproductive Assessment includes:
 - For women and men participating in activities that could lead to pregnancy, verify use of birth control for a minimum of 21 days prior to vaccination date (see Section 5.1) through the 4 months following vaccination.
 - Assess the date of the last menstrual period (LMP) for all women of childbearing potential (WOCBP) at all study visits as part of the complete PE or the targeted assessment.

Medication History:

Complete a medication history, include medication start and stop dates. Document the vaccine/placebo administration as in [Table 8](#).

Table 8 Medication Complete History or Timeframe

Medication Category	Complete History or Timeframe
Antiretroviral Therapy	Complete History
Immune-based Therapy	Current & within 105 days prior to enrollment

HCV antiviral therapy	Complete history
Prescription Drugs	Within 30 days prior to enrollment
Systemic Corticosteroids	Within 30 days prior to enrollment
HIV-1 related vaccines	Complete History
Experimental non-HIV vaccine	Within the 12 months prior to enrollment
Live attenuated vaccines	Within 4 weeks prior to enrollment
IgG therapy or immunization w/experimental Abs	Within 6 months prior to enrollment
Non-prescription drugs (OTC)	Within 30 days of enrollment

Clinical Assessments

Complete Physical Exam (PE): A complete PE will be performed at screening and Day 28. This complete PE is to include at a minimum an examination of the skin, head, mouth, and neck; auscultation of the chest; cardiac exam; abdominal exam; and examination of the lower extremity for edema. The complete PE will also include signs and symptoms, diagnosis, weight (kg), temperature (T°C, oral), respiratory rate (RR), pulse (P), and blood pressure (BP).

Targeted Physical Assessment: A targeted physical assessment is done at all other visits and includes vital signs. The targeted or directed physical assessment addresses any previously identified or new event that the participant experiences since the last study visit or any unresolved signs or symptoms previously experienced. In addition to the vital signs, this assessment includes updates to signs and symptoms, and clinical assessment of HIV disease.

Vital Signs (VS): Perform VS at all clinical visits. VS include P, BP, RR, T, and weight.

Height: Measurement of height (cm) that is required at the screening and baseline visits should be performed with shoes off.

BMI Assessment: Performed at screening for eligibility and again at Day -7 for dosing purposes.

EKG: Perform an EKG at screening for baseline assessment. The study PI (or designee) reviews the results documented in the participant's chart.

ART Adherence Assessment: This protocol requires participants take all required doses of ART. Document all missed doses, even if the reason/s for missing the doses are outside the participant's control. Report missed doses to study PI (or designee). Study participation can be terminated if HIV medication is missed.

For the purpose of this study, non-adherence is defined as missing doses for more than two (2) consecutive days or more than four (4) cumulative days in the prior 12 weeks (3 months) prior to screening visit. Assess and document any missed doses while on study and discuss missed ART doses with study PI (or designee). Continuation on study will be contingent on adherence.

Antiretroviral Medication Assessments: During the study, all modifications to the participant's ART regimen, including any ARV interruptions, dose modifications, formulations modifications, starts, and permanent discontinuations since the last study visit or at the study visit must be recorded.

Signs and Symptoms Assessments: At entry, all signs and symptoms, regardless of grade, that occurred within the 30 days before entry must be recorded.

Active solicitation of AEs will be done at every study visit. Post-entry signs and symptoms, Grade ≥ 2 , will be recorded. All signs or symptom, definitely, possibly, or probably related to study interventions will be recorded, regardless of grade. Additionally, all signs and symptoms that lead to a change in study treatment or change in ART or discontinuance of the leukapheresis procedure, regardless of grade, must be recorded.

Diagnoses: After entry, record all diagnoses identified.

Concomitant Medication Assessments: At screening and entry, record all medications taken per medical history guidelines. Thereafter, record all new or discontinued concomitant medications, including prescription, dietary supplements, and over-the-counter medications taken or stopped since the last visit.

Laboratory Studies

CD4⁺/CD8⁺: All study required absolute CD4⁺/CD8⁺ count and percentages must be obtained from a laboratory that possesses a CLIA certification or equivalent. Eligibility will be determined based on a CD4⁺ ≥ 350 at screening.

Plasma HIV-1 RNA: All study required HIV-1 RNA assays must be performed by a laboratory that possesses a CLIA certification or equivalent. Eligibility will be determined based on an HIV-1 RNA value <50 at screening.

Research Assays

Blood will be collected for the following research laboratory evaluations:

FNA and Matching Blood Sample

Analyzed for T-cell specificity, phenotype and function, and virologic measurements per the SOE. Performance of assays is dependent on cell yield and viability. Specific testing may include the following:

- Quantification of T cell memory frequencies and activation pre- and post-treatment
- Cell-associated viral RNA in CD4⁺ T cells pre- and post-treatment

Measurements of HIV specific T cell responses pre- and post-treatment Human Leukocyte Antigen (HLA) Typing

HLA testing will be performed at one time point in the study; however, if HLA type is already available in the medical record, it does not need to be repeated. The result will be used for research purposes.

Stored Plasma/PBMC for Immunology Studies: Plasma and cryopreserved PBMC will be stored for analysis of low level viremia, T-cell specificity, phenotype and function, and virologic measurements per the SOE. Specific testing will include the following:

- Low-level HIV-1 RNA assays pre- and post-treatment
- Measurement of T cell responses pre- and post-treatment
- Measurement of T cell virus inhibition pre- and post-treatment
- Phenotyping of both total and specific CD4⁺ and CD8⁺ T cell activation, homing and memory differentiation using flow cytometry pre- and post- treatment
- Functional analysis (e.g., anti-viral cytokine and lytic molecule release) of both total and specific T cells pre- and post-treatment using flow cytometry
- Cell-associated viral RNA in CD4⁺ T cells pre- and post-treatment

Site laboratory standardized protocols will guide the performance of all research assays.

NOTE: See Section 7.2.6 regarding collection of stored Plasma/PBMC for Immunology Studies for participants who discontinue ART or do not complete study treatment.

8.2 Safety and Other Assessments

8.2.1 Screening

Screening takes place in a stepwise manner and includes the completion of the following prior to enrollment:

- Informed consent (completed prior to screening assessments)
- Determination of HIV infection status
- Documentation of stable continuous ART
- Documentation of HIV RNA values that are <50 copies/mL for eligibility
- Participant locator information
- Assessment of baseline laboratory testing for continued safety monitoring

8.2.2 *Participant Enrollment*

Enrollment occurs within the 60 days following screening. Participants not meeting eligibility requirements will not continue on study. The completion of the following occurs prior to enrollment:

- Inclusion/exclusion criteria met

Once eligibility is confirmed, participant study identification numbers (SIDs) will be assigned sequentially as each participant enters the study.

8.2.3 *Leukapheresis*

Participants undergo 2 leukapheresis procedures. The first study-required leukapheresis procedure occurs at or after Enrollment/Baseline (Visit 2) but prior to Day 0. This leukapheresis provides the cells needed to perform baseline research assays and measurements required to establish pre-treatment immune responses.

NOTE: Aspirin and nonsteroidal anti-inflammatory drugs (NSAIDS) do not need to be held prior to the procedure.

The Baseline Leukapheresis

This procedure can occur at any time point within the 60 days following the Screening visit. It can occur at or after the Enrollment/Baseline (Visit 2). 0.

- If Leukapheresis procedure is scheduled on a date other than the Enrollment/Baseline visit,
 - The procedure should be scheduled after the Enrollment/Baseline visit.
 - Safety labs will be performed with the leukapheresis and not at the Enrollment/Baseline visit.
 - Complete VS and BMI assessment

- The assessments listed under the Enrollment/Baseline Visit will be done at Visit 2. Leukapheresis procedures done at UNC will have a CBC with differential done prior to the procedure (unless result available within the past 24 hours) as this is required for the Apheresis Lab.

If the leukapheresis procedure is done on the Enrollment/Baseline visit, collect the leukapheresis product in addition to the research labs. (Reference the Study Specific Lab Manual.)

The Day 28 Leukapheresis

- If Leukapheresis cannot be done within the Day 28 Visit window due to scheduling conflicts or unforeseen issues, please contact study PI for option to see person outside the visit window, either 1 week earlier or up to 2 weeks after the Day 28 Visit window.

8.2.4 Randomization

Participants are randomized to the study Arms, assigned a RID, and receive vaccine/placebo at Day 0. Study Arm assignment is double-blinded and all randomized participants will receive either vaccine or placebo. The administration of the vaccination or placebo designates Day 0 and the calculation of the remaining visits are identified by consecutive days starting with Day 0.

Vaccine and placebo product will be indistinguishable. Site and laboratory personnel and study participants will be blinded with respect to the allocation of vaccine or placebo. The randomization plan will be generated centrally by the study statisticians at the UNC CFAR using computer software, and will be kept concealed from the study personnel.

8.2.5 Participants randomized to receive study product and do not receive the vaccine/placebo or are withdrawn from the study after receipt of the vaccine (reference protocol sections 7.2 and 7.3) will be replaced and the RID re-assigned at the time of next eligible participant randomization. Study Un-blinding

Study un-blinding will occur following an independent SMC review commencing approximately 28 days after the last participant receives their vaccine/placebo injection and completes the 2nd leukapheresis.

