7 STUDY INTERVENTION DISCONTINUATION AND PARTICIPANT DISCONTINUATION/WITHDRAWAL

7.1 Discontinuation of Study Intervention

Premature Treatment Discontinuation Evaluations

There is only one study treatment intervention visit at Day 0. The collection of safety labs, virologic, immunologic, SCA, and the 2nd leukapheresis will continue to be collected per SOE, section 1.3.

Participants who complete the vaccine/placebo injection but do not complete the Day 7 study visit will be replaced, provided the inability to complete the Day 7 visit is not due to a study-related AE.

Participants who complete the vaccine/placebo injection but do not complete the Day 28 study visit and 2nd leukapheresis procedure will be replaced, provided the inability to complete the Day 28 visit is not due to a study-related AE.

Participants who receive vaccine/placebo but are unable to complete the Day 7 or 2nd leukapheresis should be encouraged to continue on study for safety assessments per the SOE.

Discontinuation of Antiretroviral Therapy

If the participant discontinues ART prior to DAY 0, DO NOT give the vaccine/placebo injection. DO NOT collect research labs for the time points after the participant discontinued ART. This participant will be replaced.

If the participant discontinues ART after the vaccine or placebo administration (Day 0), the participant should continue on study for safety follow-up as noted in the SOE. Collection of virologic, immunologic, SCA, and the 2nd leukapheresis samples will be determined on a case-by-case basis in discussion with the protocol team. This participant may be replaced.

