7.2 Participant Discontinuation/Withdrawal from the Study

1. Enrolled Participants, who are not Randomized and Do Not Start Study Treatment
 - a. Participants who withdraw or who are withdrawn from the study after the Enrollment Visit but prior to receipt of vaccine/placebo:
 - DO NOT re-use the SID.
 - REPLACE the participant.
 - b. A participant who is unable to complete the leukapheresis procedure or from whom < 40 ml is collected prior to Day 0 will be terminated from the study.
 - DO NOT re-use the SID.
 - REPLACE the participant.
 - Termination can occur due to complications at the leukapheresis procedure as determined by the Clinical PI (or designee) and the Apheresis Medical Director and can include contraindications for further leukapheresis procedures.

- c. Participants who complete the first leukapheresis procedure pre-vaccine but do not want to do the second leukapheresis procedure will be withdrawn from the study.
 - DO NOT re-use the SID.
 - REPLACE the participant.
2. Evaluations for Randomized Participants Who Do Not Start Study Treatment
 - a. Participants who withdraw or are withdrawn after randomization but prior to starting study treatment (vaccine or placebo) will have no further evaluations or follow-up.
 - Notify IDS of the withdrawal and the randomization assignment.
 - RE-ASSIGN the Randomization Identification (RID).
 - DO NOT re-use the SID.
 - REPLACE the participant.
3. Evaluations for Randomized Participants Who Received Study Product and are Discontinued or Withdrawn from Study Participation.
 - a. Participants who withdraw or are withdrawn after randomization and prior to Day 28, will have no further research evaluations or follow-up (based on review by PIs) but will be encouraged to complete EOS safety evaluation visit.
 - Notify IDS of the withdrawal and the randomization assignment.
 - REASSIGN the RID.
 - DO NOT re-use the SID.
4. A participant may withdraw or be withdrawn from the study if any of the following occurs:
 - Request by the participant to withdraw from the study and study procedures.
 - Development of an illness that requires treatment with medications prohibited in this study.
 - Change in the participant's medical condition that might make continuation in the study harmful to participant.
 - Participant does not continue to meet eligibility requirements.
 - Participant does not complete Day 7 research assays.

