 - Request of the participant's primary care provider if she/he thinks the study is no longer in the best interest of the participant.
 - Participant judged by the study Principal Investigator (or designee) to be at significant risk of failing to comply with the provisions of the protocol, as to cause harm to self or seriously interfere with the validity of the study results.
 - At the discretion of the IRB/Ethics Committee, FDA, NIH, and other government agencies as part of their duties, Principal Investigator (designee), or vaccine supplier.

Premature Study Discontinuation (D/C) Evaluations

Participants who prematurely discontinue study participation after completing the vaccine/placebo at Day 0 but before Day 70 will have premature study discontinuation (D/C visit) evaluations performed per the SOE for Day 70. Participants who discontinue the study prior to the 2nd leukapheresis without having met the primary safety outcome measure will be replaced, provided the discontinuation from study was not due to a study-related AE.

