9.2.1.1 Procedure for accounting for missing and unused data

Based on previous experience with similar trials, we anticipate that the amount of missing or invalid data will be small. All participants who are evaluable for adverse event assessment will be included in the safety analyses, regardless of whether they are replaced or missing for additional endpoints. Participants who do not start study treatment or are unable to provide the first or second leukapheresis will be replaced to achieve the planned evaluable sample size. Given the small size of this study, formal imputation methods will not be used. To assess whether key findings are sensitive to missing data, missing values can be replaced with worst possible outcomes as a sensitivity analysis (e.g., by replacing missing values in the M3 and M4 only arms with the best rank and replacing missing values in the M3+M4 arm with the worst rank, to assess if a finding regarding the M3+M4 arm is sensitive to missing data).

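### Replacement rules for dosed participants conflict on AE-related withdrawals, and re-using a dosed person's RID fixes the next randomized person's arm in advance

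*Combined protocol and SAP*

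**What the plan says.** Replacement after dosing is covered in several places.

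- **Section 7.1.** A dosed participant who misses Day 7 is replaced "provided the inability to complete the Day 7 visit is not due to a study-related AE". One who misses the Day 28 visit and second leukapheresis "will be replaced, provided the inability to complete the Day 28 visit is not due to a study-related AE".
- **Section 7.2, last paragraph.** Someone who stops before the second leukapheresis without having met the primary safety outcome is replaced "provided the discontinuation from study was not due to a study-related AE".
- **Section 7.2, item 3.** "Participants who withdraw or are withdrawn after randomization and prior to Day 28, will have no further research evaluations or follow-up". The listed actions include re-assigning the RID. There is no AE exception, and replacement is not among the actions, although items 1 and 2 list it.
- **Section 8.2.5** (the paragraph printed between Randomization and Study Un-blinding). It covers people who "are withdrawn from the study after receipt of the vaccine", refers to 7.2 and 7.3, and says they "will be replaced and the RID re-assigned at the time of next eligible participant randomization".
- **Section 9.2.1.1.** Participants "unable to provide the first or second leukapheresis will be replaced to achieve the planned evaluable sample size". There is no AE exception and no cross-reference.

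On the number itself, Section 6.3 issues the RID on Day 0 in the pharmacy, and Section 8.2.7 has staff record it at the vaccination visit. Sections 6.3 and 8.2.4 promise that the randomization plan stays concealed from study personnel. Section 6.2.3 limits routine knowledge of assignment to pharmacists. Sections 6.3 and 9.2.1.4 allow unblinding of an individual in a medical emergency.

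**The concern.** There are two separate problems.

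First, a site with one AE-related departure after dosing can find text for replacing that person and text against it. The choice decides whether another person is exposed to that arm and what the arm's safety denominator is. In a first-in-human study with 7 people per active arm and 3 on placebo, one replacement equals 1/7 = 14% of an active arm or 1/3 = 33% of placebo. That decision should not depend on which section is consulted.

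Second, handing a used RID to the next person means that this assignment is not a fresh draw. It equals the assignment of someone whose post-dose course the site has already seen. Staff who record the RID can recognize the repeat, so any impression of the first person's arm, from reactions or from unblinding, carries over. This weakens both concealment before Day 0 and blinding afterwards.

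**Working it through.** **Step 1. The rules side by side, for a dosed participant who leaves before the second leukapheresis.**

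| Section | Replace or re-assign? | Exception for a study-related AE? | Other condition |
|---|---|---|---|
| 7.1 | Replace | Yes | Missed Day 7, or missed Day 28 visit and second leukapheresis |
| 7.2, last paragraph | Replace | Yes | Primary safety outcome not met |
| 7.2, item 3 | Re-assign the RID | No | Withdrawn before Day 28 |
| 8.2.5 | Replace and re-assign the RID | No | Refers to 7.2 and 7.3; no time limit |
| 9.2.1.1 | Replace | No | Leukapheresis not provided |

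If the cause is a study-related AE, the first two rows say no and the last three say yes. The reference in 8.2.5 does not settle it, because item 3 and the last paragraph of 7.2 give different answers.

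**Step 2. What the RID carries.** The documents never state that an RID determines the arm. But it is issued at randomization, and it is re-assigned after the pharmacy is told of the withdrawal and the assignment. Re-assigning it has no evident purpose unless the arm goes with it. On that reading, the next person's arm equals the withdrawn person's arm with probability 1. For comparison, a slot drawn at random from the full 7:7:7:3 list has probability 7/24 = 29.2% for any one active arm and 3/24 = 12.5% for placebo.

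**Step 3. Does this need the AE conflict?** No. Suppose the emergency is unrelated to study product, the participant is unblinded and leaves before the second leukapheresis, and the primary safety outcome has not been met. Every row that addresses replacement then allows it, and the next arm is known to whoever learned the first.

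**Step 4. Effect on the safety figure.** The plan uses an exact one-sided 95% upper limit, the p that solves P(X ≤ x | n, p) = 0.05, equivalent to the 0.95 quantile of Beta(x+1, n−x). The plan's own figures (Section 9.2.1) reproduce:

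- 0/7: 1 − 0.05^(1/7) = 34.8% (stated 35%).
- 1/7: (1−p)^7 + 7p(1−p)^6 = 0.05 gives p = 52.1% (stated 52%).

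Now take one AE-related departure that counts as a safety event:

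- Not replaced: 1/7 = 14.3%, upper limit 52.1%.
- Replaced, both kept in the safety set, replacement event-free: 1/8 = 12.5%. Solving (1−p)^8 + 8p(1−p)^7 = 0.05 gives an upper limit of 47.1%.

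The difference is 52.1 − 47.1 = 5.0 percentage points. If the replacement also had an event, 2/8 would give an upper limit of 60.0%.

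**The case against.** The best defence is that 8.2.5 summarizes 7.2 rather than setting a rival rule, and that 9.2.1.1 is a brief missing-data paragraph while 7.1 and 7.2 are the operative sections. This would work if 7.2 spoke with one voice, but item 3 lacks the exception that the last paragraph contains. The defence narrows the conflict without removing it.

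Several stronger readings might be inferred, and the documents do not support them:

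- **That emergency unblinding is a likely route out of the study.** Nothing says so. Unblinding is confined to emergencies in which knowing the arm would alter management, is decided with independent monitoring committee members, and does not require withdrawal. Section 7.1 encourages dosed participants who miss key visits to stay for safety follow-up. Under Section 10.1.6, one possibly related SAE suspends enrollment and injections pending committee review.
- **That the site would know the arm before enrolling the next person.** The RID is issued on Day 0, after enrollment and the baseline leukapheresis. The next person will usually be enrolled already. Room to influence who is dosed next is narrower, though not absent.
- **That replacement creates an immunogenicity set of people who tolerated the product.** The departing person's later samples are missing whether or not a replacement is dosed.
- **That safety data are lost or records confused.** Section 9.2.1.1 keeps AE-evaluable participants in the safety analysis even if replaced. SIDs are never re-used, and Section 8.2.7 matches chart to treatment label by PID/SID.
- **That AE-related discontinuations would go unreported.** Section 9.3.8 already plans a table of them.

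What survives the defence is the split in the rules and the re-use of a dosed person's RID.

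**Conclusion.** The point holds in limited form. The replacement provisions for dosed participants contradict each other on AE-related departures. Independently of that, 7.2 item 3 and 8.2.5 make the next assignment a copy of the withdrawn person's. Without unblinding, staff can learn only that the two share an arm; with it, the arm itself is known.

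The size is small in expectation because few participants would be affected. Per occurrence, it is one certain assignment in place of a random draw and, in the one-event illustration, a shift of 5.0 points in a per-arm upper limit. This rests on three assumptions: that the RID carries the arm (an inference from how it is used), that both people remain in the safety set, and that the replacement has no event. It is worth correcting because concealment is an express commitment of the plan and the remedy is cheap. Nothing here shows that a planned result would be invalid.

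**What to change.** Reconcile Sections 7.1, 7.2 (item 3 and the last paragraph), 8.2.5 and 9.2.1.1 into one replacement rule. It should say whether a study-related AE or a primary safety outcome bars replacement, and up to what time point replacement applies. Which rule to adopt is for the protocol team; the need is for one rule used throughout.

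Do not re-use an RID once product has been given. The study statisticians would supply the pharmacy with new reserve RIDs for the same arm, inserted at a random position among the remaining assignments where any remain.

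The cost is a short reserve list and wording changes. One limitation remains: if a replacement is needed after the last scheduled randomization, there are no assignments left to mix it with, so its arm stays predictable to anyone who knows the withdrawn person's arm. The new number still removes the visible link for site staff.
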